### 13.2. Assessing Adverse Events

In conjunction with the medical monitor, the Investigator will evaluate adverse events to ensure the events are categorized correctly. Elements of categorization will include:

- Seriousness/Classifications (see definition in Section 13.1)
- Causality or Relatedness – i.e. the relationship between the test article, study treatment or study procedures and the adverse event (not related; unlikely related; possibly related; related - see definition in Section 13.2.1)

- Adverse Event Severity – Adverse event severity is used to assess the degree of intensity of the adverse event (mild; moderate; severe for all events - see definition in Section 0)
- Outcome – not recovered or not resolved; recovering or resolving; recovered or resolved with sequelae; recovered or resolved; death related to adverse event; unknown
- Actions Taken – none; temporarily discontinued; permanently discontinued; other

### 13.2.1. Causality Assessment

**Causality Assessment** – A determination of the relationship between an adverse event and the test article. The test article relationship for each adverse event should be determined by the investigator using these explanations:

- Not Related- An adverse event that is not related to the use of the test article, study treatment or study procedures
- Unlikely Related – An adverse event for which an alternative explanation is more likely, e.g. concomitant treatment, concomitant disease(s), or the relationship of time suggests that a causal relationship is not likely
- Possibly Related – An adverse event that might be due to the use of the test article, or to the study treatment or study procedures. An alternative explanation, e.g. concomitant treatment, concomitant disease(s), is inconclusive. The relationship in time is reasonable. Therefore, the causal relationship cannot be excluded
- Related – An adverse event that is listed as a possible adverse effect (device) or adverse reaction (drug) and cannot be reasonably explained by an alternative explanation, e.g. concomitant treatment of concomitant disease(s). The relationship in time is very suggestive, e.g. it is confirmed by de-challenge and re-challenge

### 13.2.2. Severity Assessment

**Severity Assessment** – A qualitative assessment of the degree of intensity of an adverse event as determined by the Investigator or reported to him/her by the subject. The assessment of severity is made irrespective of test article, study treatment or study procedure relationship or seriousness of the event and should be evaluated according to the following scale:

- Mild – Event is noticeable to the subject, but is easily tolerated and does not interfere with the subject's daily activities
- Moderate – Event is bothersome, possible requiring additional therapy, and may interfere with the subject's daily activities
- Severe – Event is intolerable, necessitates additional therapy or alteration of therapy and interferes with the subject's daily activities

### 13.3. Documentation and Follow-Up of Adverse Events

The recording and documenting of adverse events (ocular and non-ocular) begins when the subjects are exposed to the test article, study treatment or study procedure. Adverse events reported before the use of test article, start of study treatment, or study procedures will be recorded as medical history. However, if the condition deteriorates at any time during the study it will be recorded and reported as an AE. Untoward medical events reported after the subject's exit from the study will be recorded as adverse events at the discretion of the Investigator.

Upon finding an adverse event, the Principal Investigator will document the condition in the subject record and in the eCRFs. He/she will complete the Adverse Event /eCRF.

Complete descriptions of all adverse events must be available in the subject record. All Adverse Events including local and systemic reactions not meeting the criteria for “serious adverse events” shall be captured on the appropriate case report form or electronic data system. All adverse events occurring while the subject is enrolled in the study must be documented appropriately regardless of relationship.

It is the Investigator’s responsibility to maintain documentation of each reported adverse event. All adverse events will be followed in accordance with applicable licensing requirements. Such documentation will include the following:

- Adverse event (diagnosis not symptom)
- Drawings or photographs (where appropriate) that detail the finding (e.g., size, location, and depth, etc.)
- Date the clinical site was notified
- Date and time of onset
- Date and time of resolution
- Adverse event classification, severity, and relationship to test articles, as applicable
- Treatment regimen instituted, including concomitant medications prescribed, in accordance with applicable licensing requirements
- Any referral to another health care provider if needed
- Outcome, ocular damage (if any)
- Likely etiology
- Best corrected visual acuity at the discovery of the event and upon conclusion of the event

In addition, if an infiltrate(s) is present, he/she will complete the Corneal Infiltrate Assessment eCRF. Where necessary, a culture of the corneal lesion will be collected to determine if the infection is microbial in nature. If cultures are collected, the date of culture collection and laboratory utilized will be recorded.

Changes in the severity of an AE shall be documented to allow an assessment of the duration of the event at each level of intensity to be performed. Adverse events characterized as intermittent require documentation of the onset and duration of each episode. Changes in the assessment of relationship to the Test Article shall also be clearly documented.

Subjects who present with an adverse event shall be followed by the Investigator, within licensure, until all signs and symptoms have returned to pre-treatment status, stabilized, or been satisfactorily resolved. If further treatment beyond licensure is required, the patient will be referred to the appropriate health care provider. The Investigator will use his/her clinical judgment as to whether a subject reporting with an adverse event will continue in the study. If a subject is discontinued from the study, it will be the responsibility of the Investigator to record the reason for discontinuation. The Investigator will also document the adverse event appropriately and complete the Adverse Event eCRF. Any subjects with ongoing adverse events related to the test article, study treatment or study procedures, as of the final study visit date, should be followed to resolution of the adverse event or until referral to an appropriate health care provider, as recommended by the Investigator. Non-

ocular adverse events that are not related to the test article, study treatment, or study procedures may be recorded as “ongoing” without further follow-up.

### **13.4. Reporting Adverse Events**

The Investigator will notify the Sponsor of an adverse event by e-mail, facsimile, or telephone as soon as possible and no later than 24 hours from discovery for any serious /significant adverse events, and 2 days from discovery for any non-significant adverse event. In addition, a written report will be submitted by the Principal Investigator to the IEC/IRB according to their requirements (Section 13.4.2). The report will comment whether or not the adverse event was considered to be related to the test article, study treatment or study procedures.

#### **13.4.1. Reporting Adverse Events to Sponsor**

##### **Serious/Significant Adverse Events**

The Investigator will inform the sponsor of all serious/significant adverse events occurring during the study period as soon as possible by e-mail, fax, or telephone, but no later than 24 hours following discovery of the event. The Investigator is obligated to pursue and obtain information requested by the Sponsor in addition to that information reported on the eCRF. All subjects experiencing a serious/significant adverse event must be followed up and all outcomes must be reported.

When medically necessary, the Investigator may break the randomization code to determine the identity of the treatment that the subject received. The Sponsor and study monitor should be notified prior to unmasking the test articles.

In the event of a serious/significant adverse event, the Investigator must:

- Notify the Sponsor immediately
- Obtain and maintain in the subject’s records all pertinent medical information and medical judgment for colleagues who assisted in the treatment and follow-up of the subject
- Provide the Sponsor with a complete case history which includes a statement as to whether the event was or was not related to the use of the test article
- Notify the IEC/IRB as required by the IEC/IRB reporting procedure according to national regulations

##### **Unanticipated (Serious) Adverse Device Effect (UADE)**

In the event of an Unanticipated (Serious) Adverse Device Effect (UADE), the Investigator will submit a report of the UADE to the Sponsor and IEC/IRB as soon as possible, but no later than 24 hours after the Investigator first learns of the effect. This report is in addition to the immediate notification mentioned above.

The Sponsor must conduct an evaluation of the UADE and must report the results of the evaluation to FDA, the IEC/IRB and participating Investigators within 10 working days after the Sponsor first receives notification of the effect.

##### **Non-Serious Adverse Events**

All non-serious adverse events, including non-serious adverse device effects, will be reported to the sponsor by the Investigator no later than 2 days from discovery.

### **13.4.2. Reporting Adverse Events to the Responsible IEC/IRB and Health Authorities**

Adverse events that meet the IEC/IRB requirements for reporting must be reported within the IEC/IRB's written guidelines. Each clinical site will refer to and follow any guidelines set forth by their Approving IEC/IRB. Each clinical site will refer to and follow any guidelines set forth by their local governing Health Authorities.

The Sponsor will report applicable Adverse Events to the local health authorities according the written guidelines, including reporting timelines.

### **13.4.3. Event of Special Interest**

None.

## **13.5. Reporting of Pregnancy**

Subjects reporting pregnancy (by self-report) during the course of the study will be discontinued after the event is recorded as an Adverse Event. Once discontinued, pregnant participants and their fetuses will not be monitored for study related purposes. At the Investigator's discretion, the study participant may be followed by the Investigator through delivery. However, this data will not be collected as part of the clinical study database. Pregnant participants are not discontinued from contact lens or solution related studies for safety concerns, but due to general concerns relating to pregnancy and contact lens use. Specifically, pregnant women are discontinued due to fluctuations in refractive error and/or visual acuity that occur secondary to systemic hormonal changes, and not due to unforeseen health risks to the mother or fetus.

## **14. STATISTICAL METHODS**

### **14.1. General Considerations**

Statistical Analysis will be undertaken by the sponsor or under the authority of the sponsor. A general description of the statistical methods to be implemented in this clinical trial is outlined below. More details will be provided in the stand-alone Statistical Analysis Plan (SAP). The SAP will be finalized and signed prior to the database lock.

All data summaries and statistical analyses will be performed using the SAS software Version 9.4 or higher. Throughout the analysis of data, the results for each subject/eye will be used when available for summarization and statistical analysis.

Summary tables (descriptive statistics and/or frequency tables) will be provided for all baseline variables, efficacy variables and safety variables as appropriate. Continuous variables will be summarized with descriptive statistics (n, mean, standard deviation [SD], median, minimum and maximum). Frequency count and percentage of subjects or eyes within each category will be provided for categorical data.

### **14.2. Sample Size Justification**

The sample size was calculated to test for non-inferiority of the Test relative to Control eye drops with respect to the ocular comfort score using VAS with a minimum power of 85% and a two-sided type I error of 0.05. Assuming a difference between the Test and Control of 20, a common standard deviation (SD) of 35, the estimated sample size for non-

inferiority was 56 per treatment group using two-sample t-test. The sample size calculation was performed using the SAS procedure PROC POWER. The common standard deviation considered was based on results from [REDACTED] in which the estimated standard deviation of change in ocular end of day comfort from baseline at 30-day in the control group was estimated to be 2.53 in a VAS scale from 0 to 10 [REDACTED]

[REDACTED] We increased the standard deviation by one unit in case more variation will be observed in the Test group. Therefore, the standard deviation used in the sample calculation was 35 in a VAS scale from 0 to 100 ( $35 = 10 * (2.5 + 1)$ ).

The plan is to enroll 150 eligible subjects (60 per arm) with a target completion of 112 (56 per arm). During the enrollment period, the subject dropout rate will be closely monitored, if unexpectedly high dropout rate is observed (>10%) in certain arm(s), the targeted total enrollment number might be increased accordingly in order to ensure a minimum of 56 subjects per group to complete the 1-month follow-up.

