### **2.3. Hypotheses**

#### **Primary hypotheses:**

1. The Test eye drops will be non-inferior to the Control eye drops with respect to change in ocular comfort from baseline at 30-Day follow-up. A non-inferiority margin of -20 point ocular comfort VAS scale will be used.

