## **10. DEVIATIONS FROM THE PROTOCOL**

Investigator will notify study sponsor upon identification of a protocol deviation. Major protocol deviations must be reported to the sponsor within 24 hours after discovery of the protocol deviation. The Investigator will report deviations per IRB/IEC requirements. All deviations will be tracked and corrective actions implemented as appropriate.

If it becomes necessary for the Investigator to implement a deviation to eliminate an immediate hazard to the trial subject, the Investigator may implement the deviation immediately without notification to the sponsor. Within 24 hours after the implemented deviation, the Investigator must notify and provide the rationale to the Sponsor and, as required, the IEC/IRB.

The prescribed visit window for Visit 2 is 7 +/- 1 days from Visit 1 (Day 0), and for Visit 3 is 30 +/- 2 days from Visit 1. Subjects that complete Visit 2 five (5) days or nine (9) days from Visit 1, or complete Visit 3 twenty-seven (27) or thirty-three (33) days from Visit 1, will be categorized as a minor protocol deviation. Subjects completing Visit 2 at 4 days or earlier or 9 days or later from Visit 1 will be categorized as a major protocol deviation. Subject completing Visit 3 at 27 days or earlier, or 34 days or later from Visit 1 and these subjects or completing Visit 3 at 27 days or earlier will also be categorized as a major

protocol deviation. These subjects with major PDs will be excluded from the primary study analysis.

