##### **Per-Protocol (PP) Population:**

All subjects who have successfully completed all visits and did not substantially deviate from the protocol as determined by the trial cohort review committee prior to database lock. Justification of excluding subjects with protocol deviations from the Per-Protocol Population set will be documented in a memo to file. Per Protocol will be the primary analysis population.

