#### **Hypothesis Testing:**

The null and alternative hypotheses for non-inferiority of Test relative to Control are as follows:

$$H_0: \Delta \leq -20$$
$$H_A: \Delta > -20,$$

where  $\Delta$  is the difference between treatment groups in mean change from baseline at 30-Day follow-up (Test minus Control). The non-inferiority test will be based on the least square mean change difference and corresponding 95% confidence interval from the final model. The lower bound of the 95% confidence interval will be compared to the non-inferiority margin of -20. If the lower bound is greater than -20, the null hypothesis will be rejected, and the Test will be considered non-inferior to Control. The primary analysis will be conducted on the Per-Protocol Population. As sensitivity analysis will be conducted on the ITT Population.

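### The 85% minimum power is not secured at the completion target: 56 per arm is the number needed in the primary analysis, but it is planned as completers, with no allowance for Per-Protocol exclusions

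*Combined protocol and SAP*

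**What the plan says.** Section 14.2 asks for a "minimum power of 85% and a two-sided type I error of 0.05" and derives 56 per group from a two-sample t-test. Its planning line reads "Assuming a difference between the Test and Control of 20, a common standard deviation (SD) of 35". The same section then uses 56 per arm as the number who should finish, and foresees a possible increase in enrolment "in order to ensure a minimum of 56 subjects per group to complete the 1-month follow-up". The synopsis, sections 4.1 and 4.3 and Table 1 also give 112 (56 per arm) as the number remaining after withdrawals and losses to follow-up, from 60 randomised per arm.

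The primary analysis set is narrower. Section 14.3 makes Per-Protocol the primary population and defines it as "All subjects who have successfully completed all visits and did not substantially deviate from the protocol". Section 14.5 confirms that the primary non-inferiority test uses this set. Section 10, after classifying out-of-window visits, adds: "These subjects with major PDs will be excluded from the primary study analysis".

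Section 8.1 defines a completer as someone who consented, is eligible, attended all visits and was not withdrawn for a reason listed in section 8.2. It does not require visits to fall inside their windows.

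**The concern.** The power calculation concerns subjects who enter the primary test, whereas the recruitment plan concerns subjects who finish. These are different counts whenever a subject finishes but has a major deviation, for example a visit well outside its window. Such a subject counts toward the 56 in Table 1 and not toward the 56 in the t-test.

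The step from 60 to 56 per arm is assigned to withdrawal and loss to follow-up. Nothing is set aside for exclusions among those who complete, and no expected exclusion rate is stated. At stake is whether the quoted minimum power describes the design and analysis set as planned. Type I error is not affected.

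**Working it through.** **Inputs.** Power at least 85% and two-sided alpha 0.05 (14.2). The decision rule is "The lower bound of the 95% confidence interval will be compared to the non-inferiority margin of -20" (14.5), which is a one-sided test at 0.025. The margin comes from section 2.3: "A non-inferiority margin of -20 point ocular comfort VAS scale will be used". SD 35 and 1:1 allocation are from 14.2 and Table 1. The planning line in 14.2 words the 20 points as a difference between arms, but the stated size reproduces only if 20 is the margin and the true difference is 0.

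**Formula.** For n1 and n2 analysed subjects:

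- SE = 35 × √(1/n1 + 1/n2)
- noncentrality = 20 / SE
- degrees of freedom = n1 + n2 − 2
- power = P(noncentral t > t quantile at 0.975)

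**Step 1: reproduce the plan.** With 56 per arm, SE = 35 × √(2/56) = 6.614, noncentrality = 20/6.614 = 3.024, df = 110, critical value 1.982, power 85.02%. With 55 per arm the power is 84.4%. So 56 is the smallest equal-arm size that meets the minimum, and the plan's figure is confirmed.

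**Step 2: remove completers from exactly 56 per arm.** The exclusion rates are assumptions.

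| Situation | Analysed per arm | SE | Noncentrality | Power |
|---|---|---|---|---|
| No exclusions | 56 / 56 | 6.614 | 3.024 | 85.02% |
| One exclusion, one arm | 56 / 55 | 6.644 | 3.010 | 84.7% |
| 5% excluded (56 × 0.95 = 53.2) | 53 / 53 | 6.799 | 2.942 | 83.0% |
| 10% excluded (56 × 0.90 = 50.4) | 50 / 50 | 7.000 | 2.857 | 80.8% |

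**Step 3: does another provision fill the gap?**

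- *Randomised number.* 60 to 56 is 4/60 = 6.7%, assigned to dropout. If all 60 completed, four exclusions per arm would still leave 56.
- *Dropout trigger.* The increase in 14.2 is optional and starts only above 10%. Exactly 10% dropout leaves 60 × 0.90 = 54 completers per arm (83.7%) with no trigger, before any exclusion. A further 5% or 10% excluded leaves 51 or 48 per arm (81.5% or 79.1%).
- *The figure of 150.* Sections 4.1, 4.3 and 14.2 attach 150 subjects to 60 per arm, but 2 × 60 = 120, which is Table 1's randomisation total. Section 4.3 counts a subject as enrolled at consent, so 150 may include screen failures; section 14.2 calls the 150 eligible, and 4.1 has them randomised. The reserve, if any, cannot be read from these figures.
- *Visit windows.* Section 10 places Visit 2 at day 9, and Visit 3 at day 27, in both the minor and the major class. Until that is reconciled, the number excluded is not defined.

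**The case against.** A reader might infer that the trial fails to deliver 85% power. The documents do not support that. They give no exclusion rate, so the size of the loss rests on an assumption; at 5% it is about 2 points. More than 56 per arm may complete, and sections 4.3 and 8.2 allow an additional subject when one discontinues.

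A reader might also infer that the design has no slack at all. At the planning SD and exactly 56 analysed per arm that is true, but the SD itself is conservative. The source value was 2.53 on a 0–10 scale, or 25.3 on the 0–100 scale, and section 14.2 explains: "We increased the standard deviation by one unit in case more variation will be observed in the Test group". At SD 25.3, even 50 per arm gives 97.5%. That increase was made for variability in the Test arm and not for exclusions, and the 85% is claimed at SD 35, so it softens the point without answering it.

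Thirdly, not every protocol violator is lost from the 56. Ineligible subjects, and those withdrawn for non-compliance under section 8.2, are already non-completers under section 8.1. The gap is mainly out-of-window visits and other major deviations in subjects who finish, so an assumed rate should not count the others again.

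These points limit the size of the problem. They leave standing that the sized number and the planned number refer to different sets.

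**Conclusion.** The concern holds in a limited form. The arithmetic in 14.2 is right for 56 analysed subjects per arm, but at the completion target the stated minimum holds only if no completer is excluded from the Per-Protocol set. It is not secured; it has not been shown to be missed.

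Under assumed exclusion of 5% to 10% of completers, power at the completion target is about 83% to 81%, a loss of about 2 to 4 points. This rests on the plan's own t-test basis, SD 35, a true difference of 0 and exactly 56 completers per arm. A smaller SD or more completers would reduce or remove the shortfall; dropout above the 6.7% allowed would enlarge it.

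**What to change.** 1. In section 14.2, keep 56 per arm as the completion target, and say that 85% power applies to 56 Per-Protocol evaluable subjects per arm.
2. State an assumed Per-Protocol exclusion rate among completers, and give the power at the completion target under it: for example about 83% at 5% and about 81% at 10%.
3. When monitoring against 56, count Per-Protocol evaluable subjects as well as completers.
4. Reconcile 150 with 60 per arm (120 randomised) in the synopsis and in sections 4.1, 4.3 and 14.2.
5. Reconcile the section 10 windows that place Visit 2 at day 9 and Visit 3 at day 27 in both deviation classes. Items 4 and 5 both determine how many subjects reach the primary analysis.

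The cost is wording and one extra count during monitoring; the stated power becomes slightly less favourable. No extra subjects are needed for this version. If the sponsor would rather keep 85% on the primary set, the completion target itself must rise: 56/0.95 = 58.9, so 59 per arm at 5% exclusions, or 56/0.90 = 62.2, so 63 per arm at 10%. Randomisation would rise with it.
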